7.2 Incidence and Grade of Chest Wall Pain

Patients will be assessed at each routine follow up for development and or resolution of any chest wall pain/discomfort within the 50% isodose line. This will be graded per modified CTCAE v.5.

7.3 Detection of Rib/Vertebral Body fractures

The incidence of rib and or vertebral fractures within the radiation treatment field within the 50% isodose line will be collected from standard follow-up CT imaging at 3, 6, 9, and 12 months post SBRT.

7.4 Urine Biomarkers of Osteoclastic Activity and Bone Turnover

A single urine sample will be collected at baseline and at each follow up point (3,6,9,12 months). Samples will be collected in clinic and immediately transported to the laboratory of [name] on campus for storage in an minus 80 degrees C freezer designed for lab specimen storage. Urinary N-telopeptide (U-NTX) will be measured using ELISA based on an immobilized synthetic peptide with a specific sequence of amino acids matching a section of the N telopeptide (NTX) of type 1 collagen. Samples will be destroyed in biohazard waste immediately after analysis is complete.

The following detailed information on collection and analysis is provided from pacific biomarkers
<https://pacbio.com/ biomarker/assay-detail/148/>

Specimen Type: Urine (2nd morning void preferred; do not add preservative)

Optimum Volume: 1 mL

Stability:

2-8°C	-20°C	-70°C
1 week	3 months	1 year

Reporting units: nM BCE/mmol Cr (normalized)

Method: ELISA

Biological or Clinical Significance:

Bone resorption is a function of osteoclasts. These cells remove the mineral from bone and break down the organic matrix that is primarily comprised of type I collagen. Collagen is a cross-linked fibrous protein that forms the fabric of bone and most other connective tissues. Bone contains three polypeptide chains wound together in a helical structure. The ends of these chains (known as telopeptides) provide the intermolecular cross-linking that gives collagen its strength and resiliency. As these cross-linked domains from bone and other skeletal connective tissues are broken down, the pyridinoline cross-linking domains are released and ultimately excreted into the urine in the form of small peptides bound to pyridinoline (70%) and free pyridinoline (30%). One type of peptide-bound pyridinoline is the cross-linked N-telopeptide (NTX) which is unique to type I bone collagen. NTX can be used to identify fast losers of bone, to monitor therapy, to measure dose response, or to determine patient compliance with therapeutic prescription(s).

A growing body of clinical studies has shown that urinary NTx provides a sensitive marker of human bone resorption. Its specificity is based on originating solely from type I collagen, being particularly enriched as a cross-linking structure in bone type I collagen and being produced directly as a proteolytic neoepitope by osteoclast activity during bone resorption. Analysis of urine specimens has certain advantages, including ease of collection and reduced biohazard precautions for clinical laboratory personnel than with bloodbased specimens. However, the obtained results need to be normalized to creatinine.

Principle of Test Method:

The NTX assay is a competitive, enzyme-linked immunosorbent assay (ELISA) for the quantitative measurement of the NTX in human urine. NTX is reported as a normalized ratio to urinary creatinine in order to account for variations in urine flow rate. Therefore NTX and urine creatinine are preferably tested from the same aliquot.

7.5 Evaluable for toxicity:

All patients will be evaluable for toxicity from the time of their first treatment with risedronate, which will be given prior to start of SBRT

8.0 Adverse Events List and Reporting Requirements

8.1 Adverse Event List for Stereotactic Body Radiotherapy (SBRT)

Likely risk and side effects

- Fatigue
- Redness of irritation of the skin in the treatment area
- Hair loss in the treatment area
- For tumors near the esophagus, irritation of the esophagus and sore throat/difficulty swallowing
- Some soreness of the ribs with an increased risk of rib fracture
 - Treatment for such symptoms usually consists of rest, heat, and pain medication.
- Damage to surrounding normal lung and/or collapse of a portion of treated lung
- Changes in the lungs as the tumor shrinks
 - This includes expected "scarring".
 - In most patients, no noticeable symptoms will result from this lung damage.

Less likely risk and side effects

- Cough
- Difficulty breathing
 - Decrease in lung function parameters
 - Which may result in temporary or permanent need for supplemental oxygen
- Increased phlegm production
- Fever
- Severe pain or skin damage leading to an open wound
- Damage to the stomach or bowel
 - This can lead to ulceration or perforation with a risk of infection and death.
- Damage to the spinal cord
 - can cause numbness, weakness, tingling, and/or inability to use the arms and/or legs

- Damage to the large blood vessels surrounding the heart
 - This could cause coughing up of blood and possibly death
- Damage to the heart muscle, which can cause heart attack, heart failure, or death
- Damage to the lining of the heart, which can cause fluid accumulation around the heart
 - This may cause chest pain, shortness of breath, and/or irregular or rapid heart beat
- Tumors near vertebrae there is increased risk of vertebral compression fracture
 - If vertebral fracture is already present, there is risk of progression of fracture.
- With any radiation therapy, there may be a very small chance that the radiation could cause a secondary cancer. The excess cancer risk from the radiation is estimated to be about 3.416% with at least 7 years between the receipt of radiation and the second cancer forming. The lifetime cancer risk is about 20% assuming several decades of follow-up.
- No additional scans outside of standard of care will be taken for this study.

8.2 Adverse Event List for Risedronate

Likely risk and side effects

- Bone and joint pain
- Abdominal discomfort/indigestion

Uncommon/Rare risk and side effects

- Eye pain, redness, swelling, sensitivity to light and or decreased vision
- Glossitis
- Jaw osteonecrosis with pain in the mouth or teeth
- Numbness or feeling of heaviness in the jaw
- Poor healing of gums
- Loose teeth

Very rare

- Allergic and skin reactions
 - Hives, rash with or without blisters
 - Facial/tongue/lip swelling, trouble swallowing or breathing
- Symptoms of low blood calcium (Numbness, tingling, muscle spasms)

8.3 Adverse Event Characteristics

- **CTCAE term (AE description) and grade:** The descriptions and grading scales found in the revised NCI Common Terminology Criteria for Adverse Events (CTCAE) version 5.0 will be utilized for AE reporting. All appropriate treatment areas should have access to a copy of the CTCAE version 5.0. A copy of the CTCAE version 5.0 can be downloaded from the CTEP web site (<http://ctep.cancer.gov>).
- A modified CTCAE 5 chest wall pain grading scale accounting for control with NSAID vs Narcotic, gabapentin, or nerve block use is included in Appendix K
- We have no mechanistic reason to suspect that concurrent use of risedronate with radiation will increase pulmonary toxicities and these medications are not contraindicated during SBRT. Preliminary review of our own small retrospective database of patients concurrently receiving SBRT while on bone anti-resorptive therapies has not yielded any excess or unexpected toxicity. However, as there is only limited retrospective data in this setting, we will plan to assess for excess pulmonary toxicities once 50% of patients have been recruited and reached the 3 month followup point. If there is > 30% grade 3 or higher pneumonitis, we will discontinue the study.

- **Expectedness:**
 - AEs can be 'Unexpected' or 'Expected'
 - (see Section 7.1 above) for expedited reporting purposes only.
- **Attribution** of the AE:
 - Definite – The AE **is clearly related** to the study treatment.
 - Probable – The AE **is likely related** to the study treatment.
 - Possible – The AE **may be related** to the study treatment.
 - Unlikely – The AE **is doubtfully related** to the study treatment.
 - Unrelated – The AE **is clearly NOT related** to the study treatment.

8.4 DSMC SAE Reporting Requirements

The Data and Safety Monitoring Committee (DSMC) is responsible for reviewing SAEs for WFBCCC Institutional studies as outlined in [Appendix D](#). DSMC currently requires that all unexpected 4 and all grade 5 SAEs on these trials be reported to them for review. All WFBCCC Clinical Protocol and Data Management (CPDM) staff members assisting a Principal Investigator in investigating, documenting and reporting an SAE qualifying for DSMC reporting are responsible for informing a clinical member of the DSMC as well as the entire committee via the email notification procedure of the occurrence of an SAE.

8.5 WFUHS IRB AE Reporting Requirements

Any unanticipated problems involving risks to subjects or others and adverse events shall be promptly reported to the IRB, according to institutional policy. Reporting to the IRB is required regardless of the funding source, study sponsor, or whether the event involves an investigational or marketed drug, biologic or device. Reportable events are not limited to physical injury, but include psychological, economic and social harm. Reportable events may arise as a result of drugs, biological agents, devices, procedures or other interventions, or as a result of questionnaires, surveys, observations or other interactions with research subjects.

All members of the research team are responsible for the appropriate reporting to the IRB and other applicable parties of unanticipated problems involving risk to subjects or others. The Principal Investigator, however, is ultimately responsible for ensuring the prompt reporting of unanticipated problems involving risk to subjects or others to the IRB. The Principal Investigator is also responsible for ensuring that all reported unanticipated risks to subjects and others which they receive are reviewed to determine whether the report represents a change in the risks and/or benefits to study participants, and whether any changes in the informed consent, protocol or other study-related documents are required.

Any unanticipated problems involving risks to subjects or others occurring at a site where the study has been approved by the WFUHS IRB (internal events) must be reported to the WFUHS IRB within 7 calendar days of the investigator or other members of the study team becoming aware of the event.

Any unanticipated problems involving risks to subjects or others occurring at another site conducting the same study that has been approved by the WFUHS IRB (external events) must be reported to the WFUHS IRB within 7 calendar days of the investigator or other members of the study team becoming aware of the event.

Any event, incident, experience, or outcome that alters the risk versus potential benefit of the research and as a result warrants a substantive change in the research protocol or informed consent process/document in order to insure the safety, rights or welfare of research subjects.

8.6 Sponsor Reporting Requirements

This study has full support of the Thoracic multidisciplinary committee and has been presented for the Disease Oriented Team (DOT) for review with core senior faculty. Additionally, we have full support of the departments of medical oncology and radiation oncology. We will be applying for R grant funding, as well as funding through the NCORP and radiation oncology institute.

9.0 Pharmaceutical Information

A list of the adverse events and potential risks associated with the investigational or commercial agents administered in this study can be found in Section 8.2. We are in the process of submitting this protocol for IND exemption through the FDA and have completed the necessary paperwork for this.

9.1 Pharmaceutical Accountability

Risedronate (Actonel) is commercially available.

9.2 Product Information for ACTONEL® (risedronate sodium) tablets

Product description: Risedronate is a pyridinyl bisphosphonate. The chemical name is [1-hydroxy-2-(3-pyridinyl)ethylidene]bis[phosphonic acid] monosodium salt. It has an affinity for bone hydroxyapatite and inhibits osteoclast mediated bone resorption.

Solution preparation:

Risedronate sodium is a fine, white to off-white, odorless, crystalline powder. It is soluble in water and in aqueous solutions, and essentially insoluble in common organic solvents. It is given orally in tablet form.

Dosage forms and ingredients:

The following information below was obtained from the product monograph from Allegran Pharma Co. Markham, Ontario L6G0B5 August 2017, Submission Control 205107

ACTONEL®

Medicinal Ingredients: Each risedronate sodium tablet for oral administration contains the equivalent of 5, 30, 35, or 150 mg of anhydrous risedronate sodium in the form of the hemipentahydrate with small amounts of monohydrate. **Nonmedicinal Ingredients** (Film-coated Tablets): Crospovidone, ferric oxide red (35 mg), ferric oxide yellow (5 and 35 mg), hydroxypropyl cellulose, hypromellose, indigo carmine (150 mg), lactose monohydrate (5, 30 and 35 mg), magnesium stearate, microcrystalline cellulose, polyethylene glycol, colloidal silicon dioxide and titanium dioxide.

Dosage Strength	Description	Packaging
5 mg	film-coated, oval-shaped, yellow tablets with "RSN" engraved on one face and "5 mg" engraved on the other	carton of 28 blister packaged tablets
30 mg	film-coated, oval-shaped, white tablets with "RSN" engraved on one face and "30 mg" engraved on the other	bottle of 30 tablets
35 mg	film-coated, oval-shaped, orange tablets with "RSN" engraved on one face and "35 mg" engraved on the other	carton of 4 blister packaged tablets
150 mg	film-coated, oval-shaped, blue tablets with "RSN" engraved on one face and "150 mg" engraved on the other	carton of 1 blister packaged tablet

Storage requirements and Stability:

All dosages are recommended for storage and are stable at controlled room temperature 20° to 25°C (68° to 77°F)

Route of administration:

Route of Administration	Dosage Form/Strength	Clinically Relevant Nonmedicinal Ingredients
oral	ACTONEL film-coated tablet 5 mg, 30 mg, 35 mg, and 150 mg	lactose monohydrate (5 mg, 30 mg and 35 mg)

Disposal:

There are no specific disposal recommendations for Actonel.

9.3 Creation of Risedronate Placebo

The Wake Forest Investigational Drug Service (IDS) Pharmacy staff under leadership of [name] PharmD, MS is currently involved with an unrelated research protocol that also utilizes 150 mg of risedronate vs placebo. Therefore, we already have the necessary infrastructure in place for creation of a look-alike placebo and randomization.

10.0 Data Management

Data Collection Form	Data Storage Location
Informed consent document	EPIC
Protocol registration form	WISER/OnCore
All CT scans imaging and reports	EPIC/PACS
Adverse event log Appendix E	Oncore
Current Medications (Appendix G)	Oncore
Medication/Placebo administration form (Appendix H)	Oncore
Specific radiation related toxicities Modified CTCAE Chest wall pain Radiation pneumonitis Radiation Fibrosis (Appendix K and the pre-filled AE log)	OnCore
Radiation Treatment Details (Appendix N)	OnCore
Cortical Thickness Change (Appendix O)	OnCore
Urine bone turn over data (Appendix P)	OnCore
Fracture Incidence (Appendix Q)	OnCore
Adverse Events Log	WISER/OnCore
Biomarkers of Bone Turnover Activity	REDCap
Pain-Associated Cytokines	REDCap

Double Blind Design

We will work cooperatively with our IDS pharmacy supplying each patient either a single tablet of risedronate 150 mg or a single tablet of placebo. We will work directly with IDS pharmacy staff [contact], to procure identical placebo tablets as well as procedures for un-blinding and drug masking. As the hospital already has an unrelated protocol utilizing 150 mg risedronate vs placebo, many of these procedures are already in place. Patients will enroll through CDPM and be randomized through OnCore, but the investigator will not have knowledge of the randomization arm to which any patient has been assigned. The dispensing pharmacy will provide blinded samples and only the pharmacy will hold keys to un-blinding. At the conclusion of the study, when all patients have completed 12 months of follow up, the investigators will be unblinded to randomization of each patient.

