2.2 Secondary Objective(s)

- 2.2.1 In addition to the primary objective, we will further analyze the remaining routine follow-up chest CT scans, for mean cortical thickness change in regions of bone that received 0 – 10 Gy, >10 – 20 Gy, > 20 – 30 Gy, > 30 – 40 Gy, and > 40 Gy at all time points including 3 months, 6 months, 9 months, and 12 months. These scans are standard of care and would be performed regardless of inclusion on this trial. This will allow us to determine the potential persistence of effects from SBRT and bisphosphonate use.
- 2.2.2 We will assess and compare the incidence and grade (per modified CTCAE v.5) of radiation induced chest wall pain within the radiation treatment portal (within the 50% isodose line) at time of each routine follow up visit (3 months, 6 months, 9 months, and 12 months post SBRT). The purpose of utilizing a placebo and double-blind design is that chest wall pain is a subjective finding. Furthermore, it is unclear if chest wall pain from radiation is directly due to bone damage, nerve damage, muscle irritation, or a combination of all of these factors. The use of placebo will help us reduce the potential for bias in pain assessment.
- 2.2.3 We will assess and compare the incidence of rib and vertebral fractures (as noted on CT imaging) that occur within 12 months of irradiation and are within the radiation treatment field. The radiation treatment field will be defined as within the 50% isodose line.
- 2.2.4 The urine concentration of an osteoclast-specific biomarker, urinary N-telopeptide (NTX) indicating osteoclast activity will be assessed prior to SBRT and at each routine follow up visit (at 3 months, 6 months, 9 months, and 12 months post SBRT).

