7.0 Measurement of Effect

7.1 Cortical Thickness Mapping Approach and Radiation Dose Mapping

We will utilize our published novel method of cortical thickness mapping as outlined below.

Ribcage and vertebral cortical thickness mapping will be performed for each patient utilizing the CT scan at time of “simulation” or treatment planning/mapping and routine standard of care follow-up imaging at 3 months, 6 months, 9 months, and 12 months, which would be performed regardless of inclusion on this study.

The bony anatomy of the thorax will be segmented for each CT scan using automated thresholding techniques and manual editing in Mimics (v16.0 Materialise, Leuven, Belgium) for Windows. Individual contours of the entire ribs and vertebral bodies from cervical (C) level C7 through thoracic (T) level T12 will be constructed in treatment planning software.

These contours will be utilized to construct 3D surfaces containing over 100,000 vertices throughout the bony thorax using Stradwin software (v5.0 Cambridge University, Cambridge, England) for Windows.

Our unique cortical bone mapping algorithm relies on a global cortical density measurement, which is factored into a piecewise defined Heaviside step function derived from the convolution of the in-plane and out-of-plane point spread functions (PSFs) of each CT scan.

The global cortical bone density for each CT scan will be determined by collecting density measurements at each vertex. The CT values along a 12 mm line normal to the cortical surface at each of the approximately 50,000 vertices of the 3D rib surfaces will be obtained and applied to the validated Ct.Th estimation model constrained by the cortical density and out-of-plane blur.

Cortical thickness maps will be constructed using the pre-SBRT planning CT scan and 3 month post-SBRT follow up CT scan for each treated patient for evaluation of the primary objective. We will similarly perform this analysis at the 6 months, 9 months, and 12 months post SBRT time points for evaluation of secondary objectives.

The received radiation doses to the surface of the ribcage at each vertex will be obtained in MIM and then registered to the corresponding Ct.Th map using iterative closest point (ICP) registration in MATLAB (v2014a, MathWorks, Natick, MA). Each rib will be subdivided into evenly spaced cylindrical subsections (30 subsections per rib) along its centerline using a custom MATLAB algorithm.

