Rib vertices from the pre-SBRT CT scans will be spatially aligned with the post-SBRT CT in 3D Slicer (v 3.6, <http://www.slicer.org>) in Windows to define homologous rib subsections on the post-SBRT CT scan. A rigid transform consisting of translation and rotation operations will be computed and applied to align the pre- and post- treatment ribcage surfaces. A series of approximately twenty-five points will be manually selected on the ribcage surface to derive each transform. An affine transform will then be computed using an iterative closest point (ICP) algorithm and applied to the transformed ribcage surface to account for geometric interscan variation. The mean dose and Ct.Th for each homologous rib region will be calculated from the Ct.Th and dose measurements at all vertices within that region.

Bone within the treatment field (within the 50% isodose line) will be segmented into homologous regions receiving dose at 10 Gy intervals, of 0-10 Gy, > 10 – 20Gy, >20 – 30 Gy, > 30 – 40 Gy, and >40 Gy, and in each region the mean cortical thickness will be calculated. The % change in cortical thickness will be compared in each region between patients who received risedronate and those who received placebo.

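### Unblinding is tied to the end of 12-month follow-up rather than to completed and locked measurements, so the text allows thickness maps with manual steps to be made with the arm known

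*Combined protocol and SAP*

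**What the plan says.** **The blind (section 10.0, Double Blind Design).** During the study "the investigator will not have knowledge of the randomization arm to which any patient has been assigned", and "only the pharmacy will hold keys to un-blinding". The blind ends at the conclusion of the study, which the same sentence defines by follow-up: "when all patients have completed 12 months of follow up, the investigators will be unblinded to randomization of each patient".

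**The reason for the blind (section 2.2.2).** "The purpose of utilizing a placebo and double-blind design is that chest wall pain is a subjective finding". Image processing is not mentioned there.

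**How thickness is measured (section 7.1).** The thoracic bones "will be segmented for each CT scan using automated thresholding techniques and manual editing in Mimics". For the pre- to post-treatment alignment, "A series of approximately twenty-five points will be manually selected on the ribcage surface to derive each transform". For the primary objective, "Cortical thickness maps will be constructed using the pre-SBRT planning CT scan and 3 month post-SBRT follow up CT scan". The 6-, 9- and 12-month maps are made in the same way for the secondary objectives. No date or deadline is given for any map, and no reader masked to arm is named.

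**Analysis timing (section 11.7).** No interim analysis of primary or secondary objectives is planned.

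**The concern.** A thickness value does not exist when the scan is taken. It exists once the bone has been segmented and edited, the surfaces aligned, and the thickness and dose maps combined. A trigger based on completed follow-up can therefore be met while measurements are still outstanding. The last patient's 12-month visit is what completes follow-up, so that patient's 12-month map is the one most likely to be open when the key is released.

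The earlier scans have no deadline either. With no interim efficacy analysis, nothing in the plan forces the 3-month maps to be made early. Processing all scans in one batch after follow-up would comply with the text.

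The blind is justified by the subjectivity of pain, and pain grading is indeed covered through follow-up. The bone measures also contain human judgement, and for them the protection can lapse before the measurement is made. An operator who knows the arm could, without intending to, edit contours slightly differently in the two groups, and any such difference would enter the comparison. It is also unclear whether the image analysts count as investigators under section 10.0.

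**Working it through.** **1. The passages side by side**

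| Question | What the supplied text gives |
|---|---|
| When does the blind end? | When all patients have completed 12 months (section 10.0) |
| Must maps, reads and assays be finished first? | Not stated |
| Must the database be locked first? | Not stated |
| Are image analysts masked to arm? | Not stated; investigators is not defined |
| Are there manual steps in the map? | Yes: segmentation editing and about 25 alignment points (section 7.1) |
| Is there a deadline for the 3-month maps? | None (section 7.1); no interim efficacy analysis (section 11.7) |

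**2. How many maps, and when**

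- Maps in total: 84 patients × 5 scans = 420. Maps for the primary: 84 × 2 = 168.
- The last patient's 3-month scan nominally precedes that patient's 12-month visit by 12 − 3 = 9 months. With the ±8-week window of the study calendar (section 6.6) adverse at both ends, the gap is 9 months less 16 weeks, about 5.3 months.
- At 5-10 patients per month (section 11.5), accrual takes 84/10 = 8.4 to 84/5 = 16.8 months. With uniform accrual, the average 3-month scan precedes the trigger by 9 + 8.4/2 = 13.2 to 9 + 16.8/2 = 17.4 months.

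There is time to make every primary map under the blind, but no requirement to do so. For the last 12-month maps there is little or no such time. If 12 months is read as calendar time, the window even lets the scan itself fall after the trigger.

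**3. The plan's own sample size (section 11.4)**

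Inputs: difference 0.22 − 0.11 = 0.11 mm, SD of change 0.20 mm, one-sided alpha 0.05, power 0.80. The standardised difference is 0.11/0.20 = 0.55. A one-sided two-sample t-test needs 41.6, that is 42 per group, with power 0.804. The plan's figure of 42 is reproduced.

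**4. Illustration of what is at stake**

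The documents give no operator-error figure, so the shifts below are assumptions. The scale is mm, as in section 11.4.

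- Standard error of the difference: 0.20 × √(2/42) = 0.0436 mm, with 82 degrees of freedom; critical t(0.95, 82) = 1.664.
- Suppose there is no true effect and affected contrasts carry a net shift b in change from baseline, always favouring risedronate. If a share f of contrasts is affected, the mean shift is f × b and the non-centrality is f × b / 0.0436.
- Type I error = P(non-central t, 82 df, > 1.664).

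| Assumed shift b | All affected | Half | A quarter |
|---|---|---|---|
| 1% of 1.35 = 0.0135 mm | 0.090 | 0.068 | 0.058 |
| 1.5% = 0.02025 mm | 0.118 | 0.079 | 0.063 |
| 2% = 0.027 mm | 0.151 | 0.090 | 0.068 |

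These shifts are about 12% to 25% of the planned 0.11 mm effect (0.0135/0.11 and 0.027/0.11). If only 12-month maps are affected, f = 0 for the primary and its type I error stays at 0.05.

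**The case against.** **Permitted is not the same as planned.** A reader might infer that some maps must be made unblinded, because the last 12-month scan itself completes follow-up. The documents do not support that. They do not say that the key is released the same day, or before the last map is processed. This objection stands: the exposure is allowed, not inevitable.

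**The primary endpoint has slack.** The last 3-month scan precedes the trigger by about 5 to 9 months and the average one by more than a year. The primary is reached only if mapping is deferred that long, and nothing says it will be. This stands, although nothing in the supplied text prevents deferral.

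**The operator's influence is limited.** Thickness comes from a model fitted along lines normal to the surface at about 50,000 vertices and constrained by cortical density. The hand-picked points give only the initial rigid alignment, and an automated iterative step refines it. The endpoint is change from baseline, so an error common to both scans largely cancels. This narrows the route mainly to segmentation editing and region matching. Some influence remains, of unknown size.

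**Fractures and urine are weaker examples.** Fracture incidence is collected at each visit from standard follow-up CTs, so most reads should precede the trigger. N-telopeptide is a quantitative ELISA with little room for judgement, and its listed stability of 1 year at −70 °C weighs against holding early samples to the end. Both points stand.

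**Safeguards may exist elsewhere.** Section 10.0 refers to pharmacy procedures for unblinding that are not reproduced, and the texts of Appendices O, P and Q are not in the supplied material. Their content could not be checked, so the finding is limited to the supplied text.

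**Conclusion.** The point holds as a gap in a stated rule. The blind ends on a follow-up milestone, the bone outcome needs manual work after each scan, and no supplied text requires that work to be finished, the data locked or the analysts masked first. The firmest exposure is the last patients' 12-month maps, a secondary endpoint. Exposure of the primary depends on deferred processing.

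A reader might infer from the table that the primary test will run at 9-15% instead of 5%. The documents do not support that. Those figures need every primary contrast to be mapped with the arm known and to carry a uniform shift of 1-2% of baseline in favour of risedronate. The shift has no source in the documents. With a quarter of contrasts affected the figure is about 6-7%, and with none affected it stays at 5%. The arithmetic shows only that a small systematic reading difference would matter at this sample size; it does not estimate a bias in this trial. The textual gap does not depend on it. The change should be made before the key is released, because masking cannot be restored afterwards.

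**What to change.** Replace the unblinding sentence in section 10.0 with wording such as: *Investigators and all staff who segment, register or read scans, grade pain or run assays remain blinded until all thickness maps, fracture reads and planned assays are complete and the database is locked; only then does the pharmacy release the randomization key.*

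This also settles whether the image analysts are covered by the blind. It changes no visit, treatment or sample size; 42 per group stands. The cost is that unblinding moves later by the time needed to process the final scans and assays. If the team already works this way, the amendment only records the practice.
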